5.1 Therapeutic regimens

5.1.1 Experimental arm

Trabectedin will be given as a 24-hour infusion every 3 weeks at a starting dose of $1.5 \text{ mg/m}^2 \text{ BSA}$, until one of the treatment withdrawal criteria has been met. Subjects receiving trabectedin are required to receive dexamethasone pretreatment at 20 mg IV, 30 minutes before starting trabectedin.

5.1.2 Control arm

Treatment in the control arm is left to the discretion of the investigator, according to local standard practice, or as referred to by your national authority (see Appendix I). Limited information on the treatment administered will be recorded.

In case of treatment interruption for reasons other than disease progression as part of this study, no other treatment is allowed before disease progression.

5.2 Drug information

5.2.1 General information

The current INN name is trabectedin. The product belongs to the class: Tetrahydroisoquinolone alkaloid. The registered trademark name for trabectedin is Yondelis®.

Trabectedin is provided as a sterile lyophilized powder for reconstitution in solution for infusion in strength of 1 mg. For further information about trabectedin, please refer to the Investigator's Brochure of Yondelis®.

5.2.2 Drug supply

Trabectedin (trade name Yondelis®) will be supplied by PharmaMar free of charge and guidelines for drug resupply will be provided in a separate document.

5.2.3 Packaging, dispensing and storage

Packaging and labelling of Trabectedin will be in accordance with Good Manufacturing Practice (GMP).

For instructions regarding drug inventory, handling, reconstitution, dilution, storage, accountability and disposal, please refer to the Guide of Preparation of Yondelis® (provided as a separate document) for trabectedin.

Trabectedin (trade name Yondelis®) will be labeled according to the current regulatory requirements.

5.2.4 Drug reconciliation procedures

Accountability of the investigational study drug(s) is under the responsibility of the investigator and can be delegated to an appropriately qualified person.

Study drug accountability should be maintained by each site. Accountability records should include receipt date, batch numbers, expiry dates, patient SeqID, use by subject, dispensing dates, quantities (lowest unit) and stock balance.

In addition to internal accountability documentation on site, EORTC study-specific accountability and drug destruction forms will be supplied for this purpose, if site-specific forms are deemed not sufficiently detailed or do not provide enough information, according to EORTC Quality Assurance criteria.

The drug accountability and destruction forms will be verified during monitoring visits.

At the end of study, when all patients have stopped protocol treatment, complete drug reconciliation per batch should be available at the site for verification by EORTC in order to allow drug destruction or return procedure.

Both the unused and expired study medication must be destroyed, upon authorization of the sponsor, according to local regulations and procedures, and a copy of the destruction form must be returned to the EORTC Headquarters.

The medication provided for this trial is to be used only as indicated in this protocol and only for the patients entered in this study.

5.3 Initial dose and schedule

Trabectedin must be administered under the supervision of a physician experienced in the use of chemotherapy. Its use should be confined to personnel specialized in the administration of cytotoxic agents.

For this trial, the recommended starting dose is 1.5 mg/m² BSA, administered as an IV infusion over 24 hours with a 3-week interval between cycles. Administration through a central venous line is strongly recommended.

All patients must be premedicated with corticosteroids such as dexamethasone 20 mg IV, 30 minutes before each trabectedin infusion; not only as anti-emetic prophylaxis, but also because it appears to provide hepatoprotective effects. Additional anti-emetics may be administered as needed.

5.4 Treatment duration

Treatment should be administered until one of the withdrawal criteria has been met (see section 5.5). There is no pre-defined limit to the number of cycles to be administered.

5.5 Withdrawal criteria

The treatment will always be discontinued in case of any of the events mentioned below, whichever comes first:

- ◆ disease progression
- ◆ excessive toxicity precluding further therapy, according to the responsible physician
- ◆ patient refusal
- ◆ pregnancy
- ◆ investigator decision based on the patient's best interest, even without documented progression
- ◆ administration of concomitant drugs not allowed by the protocol (see chapter 5.7)
- ◆ if entire study is terminated for medical or ethical reasons

Patients discontinuing therapy in the absence of progression should not receive any other anti-cancer treatment before their disease progresses, unless this is clearly not in the interest of the patient.

After progression, the treatment will be left to the discretion of the treating physician. Any anti-cancer therapy other than the study drug given as single agent before disease progression within the protocol will not be considered as part of the protocol treatment and will be considered as protocol violation.

5.6 Dose and schedule modifications

After an adverse event, patients should be under surveillance until the situation has stabilized or completely resolved.

5.6.1 Trabectedin

At each visit during the treatment period, patients should first be evaluated for the occurrence of adverse events and laboratory abnormalities.

Specific recommendations for management of these possible adverse events along with guidelines for dose delay/modification or discontinuation of study treatment are provided below.

5.6.1.1 Dose reductions

Prior to re-treatment, patients must fulfill the eligibility criteria. If any of the following events occur at any time between cycles, the trabectedin dose must be reduced to 1.2 mg/m² BSA in subsequent cycles.

- ◆ Neutropenia < 0.5 x 10⁹/L lasting for more than 5 days or associated with fever or infection.
- ◆ Thrombocytopenia < 25 x 10⁹/L
- ◆ Increase of bilirubin > ULN.
- ◆ Alkaline phosphatase > 2.5x ULN and GGT > ULN
- ◆ Increase of aminotransferases (AST or ALT) > 2.5x ULN which has not recovered to < 2.5x ULN by day 21 not explained otherwise
- ◆ Any other Grade 3 or 4 adverse reactions (such as CPK elevation, nausea, vomiting, fatigue).

In order to adequately assess the duration of these events, it is recommended to perform weekly assessments.

Once a dose has been reduced because of toxicity, dose escalation in the subsequent cycles is not allowed. If any of these toxicities reappear in subsequent cycles, the trabectedin dose must be further reduced to 1 mg/ m² BSA. In the event that further dose reductions are necessary according to the above criteria, treatment should be discontinued. Colony stimulating factors can be administered for hematologic toxicity (neutropenia or febrile neutropenia) in subsequent cycles according to local standard practice.

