2.2 End-points

Primary end-point:

- ◆ Progression Free Survival (PFS)

Secondary end-points:

- ◆ Progression Free Survival at 6 months (PFS-6), median PFS (mPFS)
- ◆ Best overall response (BOR). Objective response (CR/PR), rate and median duration. Complete response (CR), rate and median duration.
- ◆ Overall survival (OS), OS probability at 6 (OS6) and 12 months (OS12), median OS (mOS)
- ◆ Safety (CTCAE v.4.0)
- ◆ Health-related Quality of life (QoL)

3 Patient selection criteria

- ◆ Age 18 or older
- ◆ Histological diagnosis of WHO grade II (chordoid meningioma, clear cell meningioma, atypical meningioma) or WHO grade III (papillary meningioma, rhabdoid meningioma, anaplastic/malignant meningioma) according to WHO 2007 classification.
- ◆ Radiologically documented progression of any existing tumor (growth > 25% in the last year) or appearance of new lesions (including intra- and extracranial manifestations)
- ◆ No more option for local therapy (resection or radiotherapy) after maximal feasible surgery and radiotherapy
- ◆ No prior systemic anti-neoplastic therapy for meningioma (patient may have received prior radionuclide therapy)
- ◆ Measurable disease (10 x10 mm) on cranial MRI no more than 2 weeks prior to randomization.
- ◆ WHO performance status 0-2
- ◆ Adequate liver, renal and hematological function within 4 weeks prior to randomization, defined as:
 - ◆ Neutrophils $\geq 1.5 \times 10^9/L$, hemoglobin $\geq 9 \text{ g/dL}$ or hemoglobin $\geq 5.6 \text{ mmol/L}$, platelets $\geq 100 \times 10^9/L$
 - ◆ Total Bilirubin $\leq 1 \times \text{ULN}$, SGPT/ALT and SGOT/AST $\leq 2.5 \times \text{ULN}$
 - ◆ Alkaline phosphatase $\leq 2.5 \times \text{ULN}$; if alkaline phosphatase $> 2.5 \text{ ULN}$, ALP hepatic isoenzyme and/or 5-nucleotidase and/or gamma glutamyltransferase (GGT) must be within the normal range
 - ◆ Albumin $\geq 30 \text{ g/L}$
 - ◆ Serum creatinine $\leq 1.5 \times \text{ULN}$
 - ◆ Creatinine clearance $> 30 \text{ ml/min}$ as calculated by Cockcroft and Gault formula (see Appendix E)
 - ◆ Creatine phosphokinase (CPK) $\leq 2.5 \times \text{ULN}$
- ◆ Normal cardiac function (LVEF assessed by MUGA or ECHO within normal range of the institution), normal 12 lead ECG (without clinically significant abnormalities). The following unstable cardiac conditions are not allowed:
 - ◆ Congestive heart failure

- ◆ Angina pectoris
- ◆ Myocardial infarction within 1 year before registration/randomization

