5.6.1.2 Re-treatment criteria

- ◆ A maximum delay of 3 weeks from the due date for next infusion is allowed for recovery from toxicity in the preceding cycle of treatment.
- ◆ The following criteria should be met before the next infusion:

Hematological parameters	Value at day 1 of new treatment cycle
Hemoglobin	≥ 9 g/dL or ≥ 5.6 mmol/L
Platelet count	$\geq 100 \times 10^9$ /L
Neutrophil count	$\geq 1.5 \times 10^9$ /L
Serum chemistry parameters	Value at day 1 of new treatment cycle
Creatinine clearance	≥ 30 mL/min
Creatine phosphokinase	$\leq 2.5 \times$ ULN
Total bilirubin	\leq ULN
ALT or AST	$\leq 2.5 \times$ ULN
Alkaline phosphatase	$\leq 2.5 \times$ ULN
Albumin	≥ 25 g/L
Non hematological – non serum chemistry parameters	Status at day 1 of new treatment cycle
Severity of other adverse event has to recover to \leq Grade 1	

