5.6.1.3 Treatment discontinuation

In the event that more than two dose reductions are required or a delay of more than 3 weeks from the due date for next infusion are necessary, patient must go off protocol treatment.

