6.3 During treatment

The following need to be performed on day 1 of each treatment cycle or within 72 hours before:

- ◆ Clinical examination (WHO PS, blood pressure, pulse rate, body weight, and body temperature).
- ◆ Assessment of all adverse events that have occurred since the previous visit and ongoing events from previous cycles should be followed.
- ◆ Complete blood counts to include hemoglobin, white blood cells, neutrophils, lymphocytes, platelets. For the experimental arm only, additional monitoring of hematological values should occur weekly during the first two cycles of therapy, and at least once between treatments in subsequent cycles
- ◆ A serum chemistry assessment to include at least creatinine, total bilirubin, ALT, AST, ALP, CPK, albumin, LDH, sodium, potassium, glucose, calcium. For the experimental arm only, additional monitoring of serum chemistry values should occur weekly during the first two cycles of therapy, and at least once between treatments in subsequent cycles
 - ◆ If ALP > 2.5 ULN, ALP hepatic isoenzyme 5-nucleotidase and/or GGT tests must be performed; ALP hepatic isoenzyme or 5-nucleotidase and/or GGT must be within the normal range.
 - ◆ Creatinine clearance will be calculated by Cockcroft and Gault formula (see Appendix E)
 - ◆ For the serum chemistry parameters not collected on the Serum Chemistry form: in case of abnormal value please record it as adverse event on the Adverse Event forms (grade, relationship, seriousness).
- ◆ Cranial MRI every 9 weeks from randomization and if clinically indicated
- ◆ Recording of corticosteroid dose every 9 weeks
- ◆ CT thorax/abdomen only if clinically indicated; if tumorous or unclear lesions detected repeat CT every 9 weeks and if clinically indicated
- ◆ HRQoL: QLQ-C30 (v3) and the BN-20 questionnaire: regardless the treatment arm, at week 3, week 6 and week 12 after treatment start (for more information see chapter 10).
- ◆ Pregnancy test (every two cycles)

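### Section 5.6.1.1 requires the eligibility criteria to be met before re-treatment, the table in 5.6.1.2 differs from them on albumin, ALP and renal function, and no precedence is stated

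*Combined protocol and SAP*

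**What the plan says.** Two consecutive subsections set conditions for the next trabectedin infusion.

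- Section 5.6.1.1 (Dose reductions) opens with a general rule: "Prior to re-treatment, patients must fulfill the eligibility criteria". It does not restrict this to laboratory values. Section 4 points to chapter 3 for the eligibility criteria.
- Section 5.6.1.2 (Re-treatment criteria) introduces its own table with "The following criteria should be met before the next infusion". It lists nine laboratory rows and requires other adverse events to have recovered to grade 1 or less.

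Three other places bear on the same decision.

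- Chapter 3 gives the entry limits. If ALP exceeds 2.5 x ULN, "ALP hepatic isoenzyme and/or 5-nucleotidase and/or gamma glutamyltransferase (GGT) must be within the normal range".
- Section 6.3, on assessments at day 1 of each cycle, asks for further tests when ALP exceeds 2.5 x ULN and says that "ALP hepatic isoenzyme or 5-nucleotidase and/or GGT must be within the normal range".
- Section 5.6.1.3 sets the consequence of waiting: if more than two dose reductions or "a delay of more than 3 weeks from the due date for next infusion are necessary, patient must go off protocol treatment".

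No section says whether chapter 3 or the table prevails where they differ.

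**The concern.** The rule that gates each infusion of a cytotoxic drug is stated twice, with different content. A patient with albumin between 25 and 30 g/L, or with ALP above 2.5 x ULN and normal GGT, meets one list and fails the other.

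A site that goes by the list the patient fails postpones the infusion. If the value does not recover, section 5.6.1.3 takes the patient off protocol treatment once the delay passes 3 weeks. A site that goes by the other list gives the infusion. Dosing, delay and discontinuation in the trabectedin arm can therefore depend on which page a site works from, and either decision could be recorded as a deviation from the other section. What is at stake is patient safety and consistent conduct across sites.

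**Working it through.** No sample-size or power figure is involved. The check sets the passages side by side and then runs example values through each list.

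**Step 1. Compare the limits.**

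| Item | Chapter 3 (imported by 5.6.1.1) | Table in 5.6.1.2 | Stricter |
|---|---|---|---|
| Hemoglobin, platelets, neutrophils, CPK, total bilirubin | same thresholds | same thresholds | – |
| ALT and AST | 2.5 x ULN (ALT *and* AST) | 2.5 x ULN (ALT *or* AST) | same threshold, looser wording in table |
| Albumin | at least 30 g/L | at least 25 g/L | chapter 3 |
| ALP | up to 2.5 x ULN, or above it with a normal hepatic follow-up test | up to 2.5 x ULN, no exception | table |
| Creatinine clearance | above 30 mL/min | 30 mL/min or above | chapter 3, only at exactly 30 |
| Serum creatinine | up to 1.5 x ULN | no row | chapter 3 |
| Recovery of other adverse events to grade 1 or less | not listed | required | table |

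Of the nine laboratory rows in the table, three differ from chapter 3 (albumin, ALP, creatinine clearance), so 9 − 3 = 6 have the same threshold. Serum creatinine is a further difference outside those nine rows. Chapter 3 is stricter on albumin and renal function and the table is stricter on ALP, so neither list contains the other. A site cannot settle the matter by choosing the stricter section.

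**Step 2. Apply each list to example day-1 values, all else normal.**

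| Day-1 value | Meets chapter 3? | Meets table? |
|---|---|---|
| Albumin 27 g/L | no | yes |
| Albumin 24 g/L | no | no |
| ALP 3 x ULN, GGT normal | yes | no |
| ALP 3 x ULN, GGT raised (other follow-up tests also not normal) | no | no |
| Creatinine clearance exactly 30 mL/min | no | yes |
| Serum creatinine 1.7 x ULN, clearance 40 mL/min | no | yes |
| ALT 3 x ULN, AST 2 x ULN | no | no, or yes if *or* is read literally |

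Hemoglobin, platelets, neutrophils, CPK and bilirubin outside their limits fail both lists.

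**Step 3. Place the other ALP rules.** The day-1 rule in section 6.3 has the same form as chapter 3: a high ALP leads to follow-up tests that must be normal. The dose-reduction trigger in 5.6.1.1 needs ALP above 2.5 x ULN *and* GGT above ULN, so ALP 3 x ULN with normal GGT triggers no reduction. Both are consistent with the chapter 3 exception. The table alone has none.

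**Step 4. Ask whether both lists can be applied together.** For the laboratory items they can. Each list states conditions to be met before the infusion, and neither says that meeting it is sufficient. A site that required every item of both would breach neither. The 25 g/L albumin row and the clearance boundary at exactly 30 would then never operate, and the chapter 3 ALP exception would never operate at re-treatment.

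**Step 5. Read 5.6.1.1 literally.** The imported criteria include no prior systemic anti-neoplastic therapy for meningioma. If trabectedin given in cycle 1 counts as such therapy, no patient can meet this before cycle 2. They also include normal LVEF and ECG, which the summary table in section 6.5 schedules only before randomization, so sites would have no scheduled result to check at later cycles.

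**The case against.** A reader might infer that sites cannot comply with both sections, or that one section permits an infusion that the other forbids. The documents do not support that for the laboratory limits. Both lists are necessary conditions, and applying them jointly satisfies both (step 4). This limits the point to an unstated precedence with redundant limits. It does not remove it: the protocol nowhere tells sites to combine the lists, and doing so would make the 25 g/L row pointless, so it cannot be presumed to be the intention.

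A second defence is that 5.6.1.1 is a loose pointer to laboratory values and that the dedicated table directly after it is the operative rule. The fact that some chapter 3 criteria cannot be met again after cycle 1 makes this plausible. It remains an inference, because 5.6.1.1 says *must* without restriction, the table is introduced with *should*, and section 6.3 keeps the ALP exception on treatment.

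A third is that the trial's conclusion is not shown to be at risk. This stands. PFS runs from randomization (7.1.3), MRI continues every 9 weeks regardless of treatment delays (6.3.1), and the per-protocol population needs only eligibility and a first dose or start of treatment (8.2.2). It is also fair that most thresholds match and that the clearance difference is minor.

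**Conclusion.** The inconsistency is real and confined to a few items. Albumin from 25 to below 30 g/L, and ALP above 2.5 x ULN with normal GGT, are the clearest cases in which the two sources give different day-1 answers. Serum creatinine above 1.5 x ULN with adequate clearance is a third, and clearance of exactly 30 mL/min is a marginal fourth. Separately, the general reference in 5.6.1.1 cannot be met literally after cycle 1.

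The consequence is possible variation between sites in dosing, delay and, through section 5.6.1.3, discontinuation in the trabectedin arm. Its size cannot be stated, because the documents do not give the frequency of these laboratory values on treatment. Alpha, power and sample size are unaffected. The conclusion rests on taking the eligibility criteria in 5.6.1.1 to mean chapter 3, and on the absence of any precedence rule in the documents.

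**What to change.** Reconcile chapter 3, section 5.6.1.1, section 5.6.1.2 and section 6.3 so that the protocol states one set of re-treatment conditions.

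- Remove the general reference to the eligibility criteria from 5.6.1.1, or limit it to named items.
- State one position each for albumin, the ALP exception (including which follow-up tests count), serum creatinine and the clearance boundary, and use the same wording wherever the item recurs.
- Clarify whether ALT and AST must both be within the limit.
- If more than one list is kept, say which governs.

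Amending only 5.6.1.1 and 5.6.1.2 would leave the day-1 ALP rule in 6.3 unreconciled. Which limits apply is for the sponsor's clinical team to decide. The cost is a wording amendment to the protocol; the statistical design and analysis need no change.

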5.6.1.2 Re-treatment criteria

- ◆ A maximum delay of 3 weeks from the due date for next infusion is allowed for recovery from toxicity in the preceding cycle of treatment.
- ◆ The following criteria should be met before the next infusion:

Hematological parameters	Value at day 1 of new treatment cycle
Hemoglobin	≥ 9 g/dL or ≥ 5.6 mmol/L
Platelet count	$\geq 100 \times 10^9$ /L
Neutrophil count	$\geq 1.5 \times 10^9$ /L
Serum chemistry parameters	Value at day 1 of new treatment cycle
Creatinine clearance	≥ 30 mL/min
Creatine phosphokinase	$\leq 2.5 \times$ ULN
Total bilirubin	\leq ULN
ALT or AST	$\leq 2.5 \times$ ULN
Alkaline phosphatase	$\leq 2.5 \times$ ULN
Albumin	≥ 25 g/L
Non hematological – non serum chemistry parameters	Status at day 1 of new treatment cycle
Severity of other adverse event has to recover to \leq Grade 1	

5.6.1.3 Treatment discontinuation

In the event that more than two dose reductions are required or a delay of more than 3 weeks from the due date for next infusion are necessary, patient must go off protocol treatment.

5.6.1.4 Nausea and vomiting

Grade 3 or 4 vomiting and nausea are commonly reported during trabectedin treatment. All patients must be premedicated with corticosteroids such as dexamethasone. Additional anti-emetics may be administered as needed.

5.6.1.5 Injection site reactions

The use of central venous access is strongly recommended. Patients may develop a potentially severe injection site reaction when trabectedin is administered through a peripheral venous line.

There have been few reported cases of trabectedin extravasation, with subsequent tissue necrosis requiring debridement. There is no specific antidote for extravasation of trabectedin. Extravasation should be managed by local standard practice.

5.6.1.6 Rhabdomyolysis and severe CPK elevations

Trabectedin must not be used in patients with CPK $> 2.5 \times$ ULN. Rhabdomyolysis has been uncommonly reported, and severe CPK elevations were observed in 4.3% of patients treated with trabectedin monotherapy, usually in association with myelotoxicity, severe liver function test abnormalities or renal failure. Therefore, CPK should be closely monitored whenever a patient may be experiencing any of these toxicities or muscle weakness or muscle pain. If rhabdomyolysis occurs, supportive measures such as parenteral hydration, urine alkalinisation and dialysis should be promptly established, as indicated. Treatment with trabectedin should be discontinued until the patient fully recovers.

Caution should be taken if medicinal products associated with rhabdomyolysis (eg, statins) are administered concomitantly with trabectedin, since it is unknown whether the risk of rhabdomyolysis may be increased in these patients.

